### **Assessments**

At baseline (pre GOALS or EDU), week 5, week 10 (post GOALS for those who began with EDU), and at 6 months, participants will be evaluated with a multi-level battery of measures assessing:

1. Neuro-cognitive performance focusing on neuropsychological measures of complex attention, executive function and memory.
2. Functional performance on complex 'real-life' tasks involving multitasking and goal management
3. Emotional regulation and daily functioning.

*Neuropsychological Assessment:* The neuropsychological battery used in this study was developed to assess performance in cognitive domains of *complex attention and executive function* that are commonly affected by both TBI and PTSD and targeted by GOALS training. *Working Memory* will be assessed with (1) Letter Number Sequencing, WAIS IV and (2) Auditory Consonant Trigrams. *Sustained attention* will be assessed with the timed Digit Vigilance test. *Inhibition of Automatic Responding* will be assessed with DKEFS Stroop Inhibition (time and error score). *Mental Flexibility* will be assessed with: (1) Trails B and (2) DKEFS Stroop Inhibition-Switching. Performance on *verbal memory* tests will be assessed with Hopkins Verbal Learning Test - HVLT-R.

Participants' performance in cognitive domains commonly affected by TBI and PTSD, but not targeted by the intervention, will also be assessed as a marker of potential non-specific changes. *Processing speed* will be assessed with (1) Trails A, requiring rapidly connecting in order numbers on a page, and with (2) DKEFS Stroop Color Naming and (3) DKEFS Stroop Word Reading. Intellectual functions estimate will be assessed at baseline with Wechsler Test of Adult Reading- WTAR. The purpose of the WTAR is to estimate pre-morbid intellectual ability. The overall battery of neurocognitive tests will take approximately 1 hour.

*Functional Assessment:* To address the functional and ecological limitations of conventional clinical neuropsychological tests in characterizing executive dysfunction, we included functional assessments in the neurobehavioral test battery. Participants will complete complex 'real-life' functional assessment task using the Goal Processing Scale (GPS). To control for practice effects of repeated administrations GPS has three alternate forms. The GPS domains assessed include: *Planning, Initiation, Maintenance of Attention, Self-Monitoring, Sequencing and Switching Attention, Flexible Problem Solving, Memory, and Execution*.

The evaluator will videotape the GPS functional assessment if the subject agreed and signed the VA 10-3203 Consent form and continues to agree to being videotaped during the assessment. The subject has the option to refuse this without affecting participation in the study.

*Self-Report Measures:* Emotional regulation / mood disturbance measures will include Profile of Mood States, Clinician-Administered PTSD Scale (CAPS), PTSD Checklist-Military Version (PCL-M), and Difficulties in Emotional Regulation Scale. Daily Functioning measures will include: Mayo Portland Adaptability Inventory and Goal Processing Questionnaire (GPQ).

### ***Follow-up***

At 6 months post-baseline, participants will be re-evaluated with the above-described multi-level battery of measures.

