### **Research questions and Hypotheses**

Question 1: What are short and long term effects of GOALS training on neuro-cognitive performance in Veterans with co-morbid PTSD and Mild TBI?

- *Hypothesis 1:* Participants in GOALS training will demonstrate greater improvements on untrained standardized neuropsychological measures of complex attention and executive function compared to participants in EDU training.
- *Hypothesis 2:* At the six month follow-up, participants will on average demonstrate improvements on standardized neuropsychological measures of complex attention and executive function relative to their baseline performance, suggesting persistence of GOALS training benefits.

Question 2: What are short and long term effects of GOALS training in veterans with co-morbid PTSD and Mild TBI on complex real-life functional task performance and daily functioning ?

- *Hypothesis 1:* Participants who participate in GOALS training will demonstrate greater improvements on an untrained complex real-life functional task than participants who participate in control EDU training.
- *Hypothesis 2:* Participants who participate in GOALS training will report greater improvements on self report measures of functional performance in their daily lives compared to participants who participate in control EDU training.
- *Hypothesis 3:* Training benefits will persist six months post GOALS training, as measured by participants' improvements in complex functional task performance and on self-report measures of everyday functional performance, relative to their pre-GOALS performance

Question 3: What are short and long term effects of GOALS training in veterans with co-morbid PTSD and Mild TBI on self-report measures of emotional regulation?

*Hypothesis 1*: Participants who participate in GOALS cognitive training will report greater improvements on self report measures of emotional regulation compared to participants who participate in control EDU training.

*Hypothesis 2*: At six month follow-up, participants will demonstrate improvements on self report measures of emotional regulation relative to their pre-GOALS performance, suggesting persistence of training benefits.

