We will assess whether training in core executive self-regulatory control functions generalizes to improvements in emotional regulation and control in participants everyday lives as reflected by self-report measures.

The primary aim of any training is to effect long term behavioral change post intervention. Long-term follow-up will be conducted to determine which aspects of the

intervention have enduring benefits, and in which domains. We predict that the GOALS approach of training core executive self-regulatory control functions, using functionally and personally-relevant activities and goals in participants' real lives, will make it more likely for training benefits to be incorporated maintained six months after training ends. This will be reflected by maintained improvement in multiple functional domains (neurocognitive, daily functioning and emotional regulation) relative to their baseline functioning.

Rehabilitation of Executive Functioning in Veterans with PTSD and Mild TBI

Provide a list of all abbreviations used in the protocol and their associated meanings.

PTSD: Post-traumatic stress disorder

mTBI: Mild traumatic brain injury

GOALS: Goal Oriented Attentional Self-regulation training – experimental

intervention

EDU: Brain Health Education – comparison intervention

OEF: Operation Enduring Freedom

OIF: Operation Iraqi Freedom

OND: Operation New Dawn

SFVAMC: San Francisco VA Medical Center

VANCHCS: VA Northern California Health Care System

Contents

Protocol Title:		4
1.0	Study Personnel	7
2.0	Introduction	8
3.0	Objectives	11
4.0	Resources and Personnel	12
5.0	Study Procedures	14
5.	5.1 Study Design	14
5.	5.2 Recruitment Methods	16
5.3	5.3 Informed Consent Procedures	18
5.4	5.4 Inclusion/Exclusion Criteria	18
5.	5.5 Study Evaluations	18
5.	5.6 Data Analysis	19
5.	5.7 Withdrawal of Subjects	19
6.0	Reporting	20
7.0	Privacy and Confidentiality	20
8.0	Communication Plan	20
90	References	22

Protocol Title:

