3.0 Objectives

- Describe the study's purpose, specific aims, or objectives.
- State the hypotheses to be tested.

The overall aim of this proposal is to investigate potential short- and long-term effects of a cognitive training program that targets executive control functions of attentional self- regulation

and goal management, Goal-Oriented Attentional Self-regulation (GOALS), in Veterans with comorbid PTSD - mTBI and cognitive difficulties.

Aim 1: Determination of short and long term effects of cognitive training on neuro-cognitive performance:

Hypothesis 1: Participants who perform GOALS training will demonstrate greater improvements on untrained standardized neuropsychological measures of complex attention and executive function compared to participants who participate in control EDU training.

Hypothesis 2: Improvements in complex attention and executive function will be sustained at six months post GOALS training, suggesting persistence of training benefits.

Aim 2: Determination of short and long term effects of cognitive training on complex real-life functional task performance and daily functioning:

Hypothesis 1: Participants who perform GOALS training will demonstrate greater improvements on untrained complex real-life functional task performance compared to participants who participate in control EDU training.

Hypothesis 2: Participants who perform GOALS training will report greater improvements on self-report measures of daily functioning compared to participants who participate in control EDU training.

Hypothesis 3: Improvements in complex functional task performance and on self-report measures of daily functioning will be sustained at six months post GOALS training, suggesting persistence of training benefits.

Aim 3: Determination of short and long term effects of cognitive training on emotional regulation:

Hypothesis 1: Participants who perform GOALS training will report greater improvements on self-report measures of emotional regulation compared to participants who participate in control EDU training.

Hypothesis 2: Improvements on self-report measures of emotional regulation measures will be sustained at six months post GOALS training, suggesting persistence of training benefits.

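### The long-term visit is set six months after baseline, so the six-month post-GOALS persistence stated in five places is not tested in either arm

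*Protocol*

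**What the plan says.** **When the visit falls.** The Protocol (the abstract dated 03/26/2019), under Follow-up, is the one place that names a starting point for the clock: "At 6 months post-baseline, participants will be re-evaluated with the above-described multi-level battery of measures". Elsewhere the visit is simply at six months. It is listed in one series with baseline, week 5 and week 10 for both arms (Protocol, Interventions and Assessments; combined protocol and SAP, section 5.1). Section 5.4 of the combined document describes the study as lasting six months.

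**What the long-term hypotheses claim.** Five statements count from the end of training:

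- Combined protocol and SAP, section 3.0, Aim 1 Hypothesis 2: "Improvements in complex attention and executive function will be sustained at six months post GOALS training".
- Section 3.0, Aim 2 Hypothesis 3: "Improvements in complex functional task performance and on self-report measures of daily functioning will be sustained at six months post GOALS training".
- Section 3.0, Aim 3 Hypothesis 2: "Improvements on self-report measures of emotional regulation measures will be sustained at six months post GOALS training".
- Combined protocol and SAP, Abstract, which predicts that the approach "will make it more likely for training benefits to be incorporated maintained six months after training ends".
- Protocol, Research questions and Hypotheses, Question 2 Hypothesis 3: "Training benefits will persist six months post GOALS training".

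The other two long-term hypotheses in the Protocol (Question 1 Hypothesis 2 and Question 3 Hypothesis 2) refer only to the six-month follow-up and are neutral on the anchor.

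**What change is measured from.** The Abstract of the combined document uses baseline for all three domains ("neurocognitive, daily functioning and emotional regulation) relative to their baseline functioning"), and the Protocol's Question 1 Hypothesis 2 also uses baseline. Question 2 Hypothesis 3 uses the pre-GOALS visit ("on self-report measures of everyday functional performance, relative to their pre-GOALS performance"), as does Question 3 Hypothesis 2. The section 3.0 hypotheses name no reference visit.

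**The concern.** A visit timed from baseline cannot also fall six months after a course that ends five or ten weeks into the study. Because GOALS ends at a different week in each arm, it cannot fall at the same post-training interval in both arms either. Every aim has a persistence hypothesis. A report that takes its wording from section 3.0 would therefore claim a durability horizon that the schedule does not reach, and would mix two different intervals if the arms were pooled.

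This is not only a difference between document versions. Question 2 Hypothesis 3 and the Follow-up section stand in the same 2019 document.

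The reference visit is a separate, smaller matter. In the GOALS-first arm, baseline and pre-GOALS are the same visit. In the EDU-first arm they are week 0 and week 5, so change from baseline includes the EDU period. The two references answer different questions in that arm, and the documents use both.

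**Working it through.** The documents state no interval from the end of GOALS to the long-term visit, so there is no plan figure to reproduce. The check is calendar arithmetic.

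**Inputs from the documents**

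- Visit: six months after baseline (Protocol, Follow-up).
- GOALS-first: five weeks of GOALS and no further formal training (Protocol, Interventions; combined document, section 5.1). GOALS ends at week 5.
- EDU-first: five weeks of EDU, then five weeks of GOALS (same sections). The Protocol's Assessments section identifies week 10 as post-GOALS for this arm. GOALS ends at week 10.

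**Assumptions**

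- Six months = 26 weeks, and one month = 365.25/12/7 = 4.348 weeks.
- Training starts at baseline. The documents give no visit window and no training start date.

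**Formulas:** interval after GOALS = visit week − week GOALS ends. Shortfall = (26 − interval)/26.

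| Arm | Interval after GOALS | In months | Shortfall |
|---|---|---|---|
| GOALS-first | 26 − 5 = 21 weeks | 21/4.348 = 4.8 | 5/26 = 19% |
| EDU-first | 26 − 10 = 16 weeks | 16/4.348 = 3.7 | 10/26 = 38% |

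**Sensitivity**

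- Six months read as 24 weeks: 24 − 5 = 19 weeks and 24 − 10 = 14 weeks.
- Training starting 2 weeks after baseline (illustrative; the documents do not support any particular delay), with a 26-week visit: 26 − 7 = 19 weeks (7/26 = 27% short) and 26 − 12 = 14 weeks (12/26 = 46% short). Any delay widens the gap.

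**Converse check.** A visit truly six months after GOALS would fall at week 5 + 26 = 31 in GOALS-first and week 10 + 26 = 36 in EDU-first. Those are 5 and 10 weeks beyond a 26-week study, and they need a different visit date by arm. No section gives such dates.

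**Reference visit.** Assessments are at weeks 0, 5 and 10 and at six months in both arms.

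| Reference | GOALS-first: later assessments | EDU-first: later assessments | EDU period included in EDU-first? |
|---|---|---|---|
| Baseline | 3 | 3 | Yes |
| Pre-GOALS (week 0 or week 5) | 3 | 2 | No |

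Each choice gives something up. Baseline keeps the number of retests equal between arms. Pre-GOALS removes the EDU period from the change.

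**The case against.** The strongest case on the other side is that the conflict is narrow. Four of the five statements are in the combined document, v1.3 of 11-13-2014, and one of those is a prediction in an abstract rather than a visit specification. In the 2019 Protocol only one of three long-term hypotheses counts from GOALS. This is fair as far as it goes. It does not remove the conflict, because the three section 3.0 hypotheses are the formal statements of the long-term aims and the 2019 document still contradicts itself once.

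A reader might infer that the documents leave the anchor open, so that nobody can say whether there is any shortfall. They do not support that. The Follow-up section is explicit, and the document containing it is dated after the last follow-up (12/30/18, Protocol, Progress to date). The single visit series and the six-month study duration fit the same clock, although the duration phrase comes from an instruction about stable therapy and is only indirect support. Timing from the end of GOALS rests on hypothesis wording alone. What remains is that no actual visit dates are given, so visit records could still show otherwise.

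A reader might also infer that pre-GOALS must be the reference for all three aims. The documents do not require it. Change from either visit is an uncontrolled within-person change with retesting, and the six-month visit is the fourth administration in both arms. The Goal Processing Scale has alternate forms (Protocol, Functional Assessment), and section 5.6 plans a practice-effect sensitivity analysis. Neither settles the reference visit. The inconsistency is real, but the choice is a trade-off.

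**Conclusion.** The concern holds. On the only stated anchor, the long-term visit falls about 21 weeks after GOALS in GOALS-first and about 16 weeks in EDU-first, 19% and 38% short of six months. Persistence six months after GOALS is therefore not tested in either arm. The figures assume 26 weeks, training starting at baseline and five-week courses. Moderate departures change the size of the gap but do not close it.

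The consequence is limited to the long-term, within-person hypotheses: by week 10 both arms have had GOALS. A reader might infer that the main efficacy result is compromised. It is not, because the randomised GOALS-versus-EDU comparison at week 5 does not depend on this visit. Nor do the documents show that any visit was made at the wrong time. The fault is that the claimed horizon does not match the scheduled one.

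**What to change.** 1. Reconcile the five statements with the Follow-up section. Restate the horizon, and any durability conclusion, as six months after baseline: about 21 weeks after GOALS in GOALS-first and about 16 weeks in EDU-first. Label this as a change made after follow-up ended, since the last follow-up was on 12/30/18 and analysis has started.
2. Report actual weeks since the end of GOALS (median and range) by arm, and show the six-month results by arm before any pooling.
3. If visit records show that visits were in fact timed from the end of GOALS, correct the Follow-up section instead. In that case also reconcile the visit series in the Protocol's Interventions and Assessments sections, the same series in section 5.1 of the combined document, and the study duration in section 5.4.
4. Separately, reconcile the reference visit across the hypotheses. For EDU-first, state that change from baseline includes the EDU period, for example by showing change from both baseline and week 5.

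The cost is wording and a by-arm table from data already collected, with no new visits. The sponsor also gives up the six-month post-training claim for a shorter one of about 16 to 21 weeks.

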### **Data Safety Monitoring Plan**

All information will be kept confidential in accordance with all regulations as specified by the Department of Veterans Affairs. Any injuries that are a direct result of research procedures will be treated at no cost to the participant. Any adverse events will be reported immediately by the PI to the Central VA. All associated personnel will have human subjects training and certification. All patients will be given a copy of their informed consent and encouraged to ask questions if they have any concerns.

*Cognitive Testing:* There is a possibility of frustration from poor performance or fatigue. Cognitive testing will stop if a patient displays frustration or appears tired.

*Cognitive training:* There is a possibility of fatigue, frustration, or boredom from performance of cognitive tasks. Participants are allowed frequent breaks during training. For patients, training will be adjusted for the fatigue level, and training sessions will stop if patients are frustrated or fatigued. Thus far, participants have generally expressed positive experiences with training.

It is possible that participation in the study may lead to an exacerbation of PTSD symptoms. All research staff directly working with participants have previous training and experience in working with this Veteran population (e.g., neuropsychologists; neuropsychology trainees; occupational therapist, certified rehabilitation counselor, etc.). Additionally, prior to contact with subjects, all research staff will undergo investigator-led training to confirm they recognize symptoms associated with PTSD/mTBI, such as subject reports of, or behavior that reflects: re-experiencing the traumatic event, avoidance, increased anxiety, emotional arousal, anger and irritability. Research staff will be instructed to communicate such manifestations as soon as possible to the study investigators, who are licensed clinicians with expertise in the assessment and management of symptoms associated with PTSD and brain injury. A study investigator will immediately attempt to contact the subject for a telephone assessment, or if indicated, to schedule an in-person assessment. Further action will be based on an assessment of the subject. Possible actions may include referral for additional appropriate clinical evaluation and/or follow-up treatment and possibly terminating the subject's participation in the study. If a subject is withdrawn from the study due to increased symptoms, the study investigator will personally inform the subject of the decision to terminate involvement and may refer the subject to follow-up treatment if the subject is significantly distressed over being withdrawn.

In the event a subject manifests increased PTSD symptoms that are not minor and transient, the investigator will complete Form 119: Report of Unanticipated Serious Adverse Event (SAE) and/or Unanticipated Problem (UAP) Involving Risks to

Participants or Others.

If a subject expresses concern about another subject divulging personal information outside the research setting, research staff will inform the study investigator. The study investigator will then contact the subjects in question to address any breaches of privacy or confidentiality.

Research staff will notify the study investigator within 24 hours if any subjects report or manifest more than minor and transient distress. The study investigator will contact the subject to evaluate the situation and determine if clinical referral is warranted. If a referral is warranted, the study investigator will inform the subject that a referral for treatment will be made. When making the referral, the study investigator will request that the subject's privacy be respected when scheduling the appointment.

All research staff will be trained in the above procedures. The research team will also meet or have conference calls weekly to discuss study activities and any issues or concerns about subjects. The research staff at both study sites is the same.

### **Progress to date**

- Study was conducted at both SFVAMC and VA NCHCS in Martinez sites.
- Staff was hired and trained in study recruitment, assessment and cognitive training procedures.
- Study actively recruited subjects at both sites:
  - 545 letters describing the study have been mailed to potential participants; 218 detailed telephone screens have been conducted; 76 participants have been enrolled.
- To help enhance recruitment, researchers has made extensive efforts to enroll Veterans, including providing IRB-approved recruitment material to VA Outpatient clinics, Veteran Centers, State of California Department of Rehabilitation Veteran services programs, State of California Employment Development Department disabled Veterans outreach, State of California County Veterans services, community college Veteran affairs offices.
- Presentations describing the aims of this study have been made by PI and co-investigators to clinicians and researchers at both SFVAMC and VA NCHCS in Martinez, and at the: VINS21 TBI Polytrauma meeting 2014, 2015, 2016; and 2018; American College of Rehabilitation Medicine Conference October 2015; VA Psychology Leadership Conference May 2015 and May 2017; 10 World Congress on Brain Injury in April 2017; International Neuropsychological Society Meeting February 2016 ,February 2017, February 2018 and February 2019; 8th Federal Interagency Conference June 2018, and American Psychological Association Conference August 2018.
- Study is closed for enrollment, last follow-up on 12/30/18. Data analysis has started.
- Preliminary results from 40 participants who completed the training indicate that at week 5, after GOALS training, but not after EDU training, participants significantly improved on neuropsychological measures of attention/executive function, complex functional task performance and measures of emotional regulation. Participants reported incorporating trained strategies into their daily lives.
